2.1 Sample size calculation

Sample size calculations are described in the protocol section 17.1 and will not further be described here.

2.2 Definition of analysis sets

The following analysis sets are defined in accordance with the ICH-E9 guidance¹:

- **Full Analysis Set (FAS):** includes all randomised subjects. In exceptional cases, subjects may be eliminated from the full analysis set. In such cases the elimination will be justified and

documented. The statistical evaluation of the FAS will follow the intention-to-treat principle and subjects will contribute to the evaluation “as randomised”

- **Safety Analysis Set (SAS):** includes all subjects receiving at least one dose of the investigational product or comparator. Subjects in the safety set will contribute to the evaluation “as treated”

Randomised subjects who are lost to follow-up and where no exposure information of the investigational product or comparators is available after randomisation will be handled as unexposed.

Before data are released for statistical analysis, a review of all data will take place to identify protocol deviations that could potentially affect the results. Any decision to exclude any subject or observation from the statistical analysis is the joint responsibility of the members of the sponsor study group. The subjects or observations to be excluded, and the reasons for their exclusion must be documented and signed by those responsible before database lock. The subjects and observations excluded from analysis sets, and the reason for this, will be described in the clinical trial report.

2.3 Primary endpoint

The primary endpoint is defined as change from baseline in HbA_{1c} after 26 weeks of treatment.

The change from baseline in HbA_{1c} after 26 weeks of treatment will be analysed using an ANCOVA model with treatment, pre-trial anti-diabetic treatment (metformin + basal insulin, metformin + one other OAD + basal insulin, metformin + pre-mix/combination insulin, metformin + one other OAD + pre-mix/combination insulin) as fixed factors and baseline HbA_{1c} as covariate. Missing values after 26 weeks of treatment will be imputed applying LOCF using HbA_{1c} values at and after baseline.

Superiority of IDegLira vs. IDeg will be considered as confirmed if the 95% confidence interval for the mean treatment difference for change from baseline in HbA_{1c} lies entirely below 0.0%; equivalent to a one-sided test with significance level of 2.5%. Conclusion of superiority will be based on FAS.

2.3.1 Sensitivity analysis

Sensitivity analysis will be performed on FAS using the mixed model for repeated measurement (MMRM) to evaluate the robustness of using LOCF. All HbA_{1c} values available post baseline at scheduled measurement times will be analysed in a linear mixed normal model using an unstructured residual covariance matrix for HbA_{1c} measurements within the same subject. The model will include treatment, visit and pre-trial anti-diabetic treatment as fixed factors and baseline HbA_{1c} as covariate. Interactions between visit and all factors and between visit and baseline HbA_{1c} are also included in the model.

Further, a pattern mixture model approach, mimicking an intention-to-treat scenario will be applied. The imputation in the IDegLira arm will be based on IDeg values. It will be done as follows:

- In the first step intermittent missing values are imputed using a Markov Chain Monte Carlo method, in order to obtain a monotone missing data pattern. This imputation is done for each treatment group separately and 1000 copies of the dataset will be generated.
- In the second step, for each of the 1000 copies of the dataset, an analysis of variance model with treatment and pre-trial anti-diabetic treatment as fixed factors, and baseline HbA_{1c} as covariates is fitted to the change in HbA_{1c} from baseline to 4 weeks (V10) for the comparator group only. The estimated parameters, and their variances, from this model are used to impute missing values at 4 weeks for subjects in comparator and IDegLira treatment groups, based on pre-trial anti-diabetic treatment and HbA_{1c} at baseline.
- In the third step, for each of the 1000 copies of the dataset, missing HbA_{1c} values at 8 weeks (V14) are imputed in the same way as for 4 weeks. Now the imputations are based on an analysis of variance model with the same factors and the HbA_{1c} values at baseline and 4 weeks as covariates, fitted to the comparator group.
- This stepwise procedure is then repeated sequentially over the available planned visits, adding one visit in each step until the last planned visit at 26 weeks (V32)
- For each of the complete data sets, the change from baseline to 26 weeks is analysed using an analysis of variance model with treatment and pre-trial anti-diabetic treatment as fixed factors and baseline HbA_{1c} value as a covariate.

The estimates and standard deviations for data sets are pooled to one estimate and associated standard deviation using Rubin's rule³. From these pooled estimates the confidence interval for the treatment differences and the associated p-value are calculated.

The results of the sensitivity analyses will be compared to the result of the standard ANCOVA method using LOCF for imputation of missing data. Any marked difference between the MMRM, the pattern mixture approach and ANCOVA LOCF approach regarding the estimated treatment difference will be commented upon in the clinical trial report.

Additional sensitivity analysis will be performed comparing the treatment difference in subjects recruited by one set of criteria compared to ones recruited with updated set of criteria, in order to evaluate the impact of protocol amendment 2 (08-Sep-2016) implemented during recruitment of subjects.

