2.3 Calcitonin \geq 10 and < 50 ng/L

Action: The subject can continue in the trial on trial product. Continue sampling of calcitonin according to the protocol. If the subject is a screen failure or if the value is from the last sample taken in the trial, the subject should be referred to a thyroid specialist for further evaluation.

Background: Calcitonin values from 20-50 ng/L were found in up to 1% of subjects of the population of 5817 patients with thyroid nodular disease¹. The predictive value of a C-cell anomaly

for this calcitonin level was 8.3%. However, the likelihood of having a medullary carcinoma >1 cm with calcitonin in this range is extremely low.

For calcitonin values 10-20 ng/L Costante et al¹ identified 216 (3.7%) patients. One patient out of the 216 had a subsequent basal (unstimulated) calcitonin of 33 ng/L, and had C-cell hyperplasia at surgery. Two other studies used a cut-off of calcitonin > 10 ng/L to screen for C-cell disease, but they do not provide sufficient information on patients with basal calcitonin >10 and <20 ng/L to allow conclusions^{2, 3}.

3 References

Protocol Amendment
Trial ID: NN9068-4184
UTN: U1111-1178-3453
EudraCT No.: N/A

~~CONFIDENTIAL~~

Date:
Version:
Status:
Page:

30 June 2016
1.0
Final
1 of 4

Novo Nordisk

Protocol Amendment
No 1
to Protocol, final version 2.0
dated 02 May 2016

DUAL™ II Japan
Trial ID:NN9068-4184

A double-blinded trial comparing the efficacy and safety of insulin degludec/liraglutide and insulin degludec both in combination with metformin in Japanese subjects with type 2 diabetes mellitus inadequately controlled with basal or pre-mix/combo insulin therapy and oral anti-diabetic drugs

Trial phase: 3a

Applicable to Japan

Amendment originator:

, PhD

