2.1 Section 5.3.1– PMDA request for added text is implemented

2.1.1 Change:

The recommended start dose of IDegLira is 10 dose steps (10 units IDeg/0.36 mg liraglutide), with the option of choosing up to 16 dose steps (16 units IDeg/0.6 mg liraglutide) at the investigator's discretion. The 0.36 mg of liraglutide contained in the recommended starting dose almost corresponds to the approved starting dose (0.3 mg) of Victoza[®] in Japan. *The 0.6 mg of liraglutide contained in the starting 16 dose steps is different from the approved starting dose of Victoza[®] in Japan, however in consideration of each subject's safety status, including the possibility of hypoglycaemia or hyperglycaemia, up to 16 dose steps can be chosen at the investigator's discretion.* IDegLira will be titrated twice weekly according to a predefined titration algorithm to a maximum of 50 dose steps (50 units insulin degludec/1.8 mg liraglutide) aiming to reach a FPG target between 4.0 mmol/L (72 mg/dL) and 5.0 mmol/L (90 mg/dL).

2.1.2 Rationale:

The starting dose of liraglutide could potentially be 0.6 mg (at the discretion of the investigator) which is not an approved starting dose of Victoza in Japan. So PMDA request it further stated that consideration in relation to subject safety is at the discretion of the investigator when choosing up to 16 dose steps (16 units IDeg/0.6 mg liraglutide) as the starting dose.

Protocol Amendment
Trial ID: NN9068-4184
UTN: U1111-1178-3453
EudraCT No.: NA

~~CONFIDENTIAL~~

Date:
Version:
Status:
Page:

14 December 2016
1.0
Final
1 of 8

Novo Nordisk

Protocol Amendment
No 2
to Protocol, final version 3.0
dated 08 Sep 2016

Trial ID: NN9068-4184

A double-blinded trial comparing the efficacy and safety of insulin degludec/liraglutide and insulin degludec both in combination with metformin in Japanese subjects with type 2 diabetes mellitus inadequately controlled with basal or pre-mix/combination insulin therapy and oral anti-diabetic drugs

Trial phase: 3a

Applicable to Japan

Amendment originator:

, PharmD

TrialOps 2, Insulin & Devices

~~This confidential document is the property of Novo Nordisk. No unpublished information contained herein may be disclosed without prior written approval from Novo Nordisk. Access to this document must be restricted to relevant parties.~~

Table of Contents

	Page
Table of Contents.....	2
1 Introduction including rationale for the protocol amendment.....	3
1.1 Eligibility criteria update	3

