1.2 Scope of the statistical analysis plan

This Statistical Analysis Plan (SAP) is based on Final Protocol version 4.0 (15-Dec-2016).

The scope of this SAP is to specify the statistical analysis for change from baseline in body weight after 26 weeks of treatment and add sensitivity analysis for change from baseline in HbA_{1c} after 26 weeks of treatment due to protocol amendment 2 during recruitment of subjects. Furthermore, some errors have been corrected. For further details on the changes see [section 3](#).

2 Statistical considerations

Novo Nordisk will analyse and report data from all sites together.

All analyses of efficacy and safety endpoints will be based on the full analysis set (FAS). All efficacy endpoints will be summarised using the FAS and safety endpoints will be summarised using the safety analysis set (SAS).

The impact of protocol deviations and outliers may be investigated further in the sensitivity analyses if deemed relevant.

Unless otherwise specified, all continuous measurements will be summarised descriptively at each visit by treatment using observed data. After 26 weeks of treatment, descriptive statistics will be presented based both on observed and last observation carried forward (LOCF) imputed data. Endpoints that are analysed untransformed and endpoints that are not formally analysed are summarised by the arithmetic mean, standard deviation (SD), median, and minimum and maximum values. Endpoints that are analysed log-transformed are supplemented with the geometric mean and coefficient of variation (CV).

For measurements over time, mean values will be plotted to explore the trajectory over time. LOCF imputed data will be used as the basis for plotting data, if not otherwise specified. For endpoints that are analysed log-transformed, the geometric mean values will be plotted.

A standard analysis of covariance (ANCOVA) model will be applied for the continuous primary and secondary endpoints. The model includes treatment, pre-trial anti-diabetic treatment (metformin + basal insulin, metformin + one other OAD + basal insulin, metformin + pre-mix/combination insulin, metformin + one other OAD + pre-mix/combination insulin) as fixed factors and the corresponding baseline value as covariate. In the following, this model will be referred to as the standard ANCOVA model.

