2.4.2 Patient reported outcomes

The following questionnaires will be used to compare PROs between treatments:

- DTR-QOL questionnaire
- EQ-5D-5L questionnaire

The questionnaires will be summarised descriptively by visit and treatment.

For the DTR-QOL questionnaire change from baseline in the following scores will be analysed separately using the standard ANCOVA:

- Domain QOL scores
 - Burden on social activities and daily activities
 - Anxiety and dissatisfaction with treatment
 - Hypoglycemia
 - Satisfaction with treatment
- Total QOL score

For the EQ-5D-5L questionnaire change from baseline in QOL and VAS scores will analysed separately using the standard ANCOVA.

Quality Adjusted Life Years will be evaluated in a separate report by the Novo Nordisk Health Economics and Outcomes Research department.

3 Changes to the statistical analyses planned in the protocol

Corrections have been made to the supportive secondary endpoints. The description of analysis of change from baseline in body weight after 26 weeks of treatment has accidentally been left out of protocol, however listed in the endpoint section of the protocol.

Additional sensitivity analysis for change from baseline in HbA_{1c} has been added to further evaluate the impact of protocol amendment 2 (08-Sep-2016) implemented during recruitment of subjects for this trial. In this amendment inclusion and exclusion criteria was changed, therefore a sensitivity analysis comparing treatment difference in subjects recruited by one set of criteria will be compared to ones recruited with updated set of criteria.

Box plots have replaced the planned histograms for calcitonin.

4 References

1. International Conference on Harmonisation. ICH Harmonised Tripartite Guideline. Statistical principles for clinical trials E9. International Conference on Harmonisation E9 Expert Working Group. September 1998.

Statistical Analysis Plan
Trial ID: NN9068-4184
UTN: U1111-1178-3453
EudraCT No.: NA

~~CONFIDENTIAL~~

Date:	08 December 2017	Novo Nordisk
Version:	1.0	
Status:	Final	
Page:	14 of 14	

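### Does the wrong date for Amendment 2 in the SAP spoil the comparison of subjects recruited under the old and the updated eligibility criteria?

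*SAP*

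**What the plan says.** The SAP attaches the same date to Amendment 2 in two places. Section 2.3.1 says the extra analysis is there to "evaluate the impact of protocol amendment 2 (08-Sep-2016) implemented during recruitment of subjects". Section 3, which lists changes from the protocol, says it was added to "further evaluate the impact of protocol amendment 2 (08-Sep-2016) implemented during recruitment of subjects for this trial".

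The title block of Amendment 2 reads differently. The amendment is dated "14 December 2016" and applies "to Protocol, final version 3.0", "dated 08 Sep 2016". SAP section 1.2 agrees with a December amendment: "This Statistical Analysis Plan (SAP) is based on Final Protocol version 4.0 (15-Dec-2016").

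On grouping, SAP sections 2.3.1 and 3 both say that the treatment difference is to be compared between subjects recruited under one set of criteria and subjects recruited under the updated set. Neither gives a cut-off date, a named grouping variable or a model.

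**The concern.** Amendment 2 loosened eligibility while recruitment was open. The stable-treatment period fell from 90 to 60 days, the allowed insulin-dose fluctuation rose from 10% to 20%, and past GLP-1 receptor agonist use was admitted under conditions. The added analysis is the only planned check on whether this altered the treatment effect.

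The only date the SAP attaches to the change belongs to a protocol version that still held the old criteria. A programmer who took it as the dividing line would put every subject recruited from 08 September until the real switch into the wrong group. The error runs in one direction only and would blur the contrast. If the first visit fell on or after 08 September, the old-criteria group would be empty. Either way, the check on Amendment 2 would be weakened or lost.

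**Working it through.** **Which date is right.** The two amendment title blocks share a layout.

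| Amendment | Own date | Protocol version amended | Date of that version |
|---|---|---|---|
| No 1 | 30 June 2016 | 2.0 | 02 May 2016 |
| No 2 | 14 December 2016 | 3.0 | 08 September 2016 |

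In each block the date after the word dated belongs to the protocol being amended (for Amendment 1, "dated 02 May 2016"). So 08 September 2016 is the date of version 3.0. Version 4.0, on which the SAP rests, is dated one day after Amendment 2. The label in the SAP is wrong.

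**Size of the slip.** From 08 September to 14 December 2016 is 22 + 31 + 30 + 14 = 97 days, or 97/7 = 13.86 weeks. Against the 24-week recruitment period set by Amendment 2, 13.86/24 = 58%.

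**What it does if the plan is followed.** Grouping is by criteria set. The bracketed date does not enter that rule, so the number misassigned is 0.

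**What it would do if misused as a cut-off.** The first-visit date is not in the documents, so it has to be assumed. Let f be the first visit in weeks relative to 08 September, with even accrual of 210 subjects over 24 weeks and the true switch on 14 December.

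- Truly old-criteria = 210 × (13.86 − f)/24
- Labelled old-criteria = 210 × max(0, −f)/24

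| First visit | Truly old | Labelled old | Moved |
|---|---|---|---|
| 8 weeks before | 191 | 70 | 121 |
| 4 weeks before | 156 | 35 | 121 |
| 08 September | 121 | 0 | 121 |
| 4 weeks after | 86 | 0 | 86 |
| 8 weeks after | 51 | 0 | 51 |

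The 58% share is a ceiling. With a first visit 8 weeks after 08 September, the affected window is 97 − 56 = 41 days, and 41/168 = 24% of 24 weeks. Even accrual is also doubtful, because Amendment 2 was written on account of very low recruitment under the old criteria. A share of calendar time is therefore not a share of subjects.

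**Precision of the comparison.** With SD 1.0 (protocol section 17.1) and a fraction f* of the 210 subjects in one group, the standard error of the difference between the two treatment differences is √[4/(210f*) + 4/(210(1 − f*))].

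- f* = 0.5: SE 0.276, 95% half-width 1.96 × 0.276 = 0.54
- f* = 0.2: SE 0.345, 95% half-width 1.96 × 0.345 = 0.68

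Both half-widths exceed the planned completer effect of 0.45. The contrast is descriptive at best, whichever date is printed. These widths depend on the group sizes and do not measure the effect of the wrong label.

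**Primary analysis.** The planned difference is 0.85 × 0.45 + 0.15 × 0.20 = 0.4125. A two-sample t-test with 105 per arm, SD 1.0 and two-sided 5% gives power of 84.5%, as in protocol Table 17-1. No input to this is a date.

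**The case for a change.** The best case for a change is that the SAP was written in part to add this analysis, yet it leaves the grouping variable undefined. Recruited could mean consented, screened or randomised, and protocol section 8.1.5 allows up to 14 days between screening and randomisation. No model or interaction estimate is specified. The wrong date is then the only concrete anchor on the page. If the first visit was some weeks before 08 September, a split there would yield two non-empty groups and might pass unnoticed. Correcting the text would cost almost nothing.

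Part of this stands: the label is wrong in both places, and the operational detail is thin. The harm still needs an analyst to set aside the stated rule and use a parenthetical label in its place. The SAP gives enough to prevent that, since section 1.2 dates version 4.0 to December 2016 and the amendment prints its own date.

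The missing detail has a natural reading. The eligibility periods that Amendment 2 changed are counted back from screening. Protocol section 8.1.4.1 bars re-screening after a failed criterion, so a subject who failed under the old criteria cannot return under the new ones. The criteria set in force at the subject's site at screening is therefore the obvious variable.

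Printing 14 December instead would not provide a valid cut-off. Protocol section 25.1 bars implementing an amendment before approval, so the effective date may be later and may vary by site. The absence of a specified interaction model is a separate matter that does not follow from the date.

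**Conclusion.** The concern is right about the date and wrong about the consequence. SAP sections 2.3.1 and 3 give Amendment 2 the date of the protocol version it amended, 97 days too early. Because subjects are grouped by criteria set and no date serves as a cut-off, nobody is misassigned when the plan is followed. The figures of 51 to 121 subjects, and the 58% of recruitment time, apply only if the label is used against the stated rule. They also rest on an assumed first-visit date and, for the subject counts, on even accrual.

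The affected item is one supplementary sensitivity analysis with wide intervals. Sample size, power, the primary ANCOVA on the full analysis set and the superiority decision are untouched. What remains is a clerical slip and a gap that analysts fill sensibly by taking the criteria in force at screening. No change to the plan follows.

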2.4 Secondary endpoints

2.4.1 Supportive secondary endpoints

2.4.1.1 Efficacy endpoints

Insulin dose after 26 weeks of treatment

The actual daily dose after 26 weeks of treatment will be analysed using the standard ANCOVA model including treatment and pre-trial anti-diabetic treatment as fixed factors and baseline HbA_{1c} value and baseline insulin dose as covariates.

Body weight

The change from baseline in body weight after 26 weeks of treatment will be analysed using the standard ANCOVA model with treatment and pre-trial anti-diabetic treatment as fixed factors and baseline body weight as covariate. Missing values after 26 weeks of treatment will be imputed applying LOCF using body weight values at and after baseline.

Responder after 26 weeks of treatment

Two dichotomous endpoints (responder/non-responder) will be defined based on whether a subject has met a specific target level after 26 weeks of treatment:

- HbA_{1c} < 7.0%
- HbA_{1c} ≤ 6.5%

Analysis of each of the two responder endpoints will be based on a logistic regression model with treatment and pre-trial anti-diabetic treatment as fixed factors and baseline HbA_{1c} values as a covariate.

HbA_{1c} responder endpoints without weight gain after 26 weeks of treatment

Responder for HbA_{1c} without weight gain after 26 weeks of treatment will be defined as HbA_{1c} < 7.0% or ≤ 6.5% at ET and change from baseline in body weight below or equal to zero. Analysis of each of the two responder endpoints will be based on a logistic regression model with treatment and pre-trial anti-diabetic treatment as fixed factors and baseline HbA_{1c} and baseline body weight values as covariates.

HbA_{1c} responder endpoints without hypoglycaemic episodes

Responder for HbA_{1c} without hypoglycaemic episodes after 26 weeks of treatment will be defined as HbA_{1c} < 7.0% or ≤ 6.5% at ET and without treatment emergent severe or BG confirmed symptomatic hypoglycaemic episodes during the last 12 weeks of treatment. Analysis of each of the two responder endpoints will be based on a logistic regression model with treatment and pre-trial anti-diabetic treatment as fixed factors and baseline HbA_{1c} values as a covariate.

HbA_{1c} responder endpoints without hypoglycaemic episodes and weight gain

Responder for HbA_{1c} without hypoglycaemic episodes and weight gain after 26 weeks of treatment will be defined as HbA_{1c} < 7.0% or ≤ 6.5% at ET, without treatment emergent severe or BG confirmed symptomatic hypoglycaemic episodes during the last 12 weeks of treatment, and change from baseline in body weight below or equal to zero. Analysis of each of the two responder endpoints will be based on a logistic regression model with treatment and pre-trial anti-diabetic treatment as fixed factors and baseline HbA_{1c} and body weight values as covariates.

Fasting plasma glucose (FPG)

Change from baseline in FPG after 26 weeks of treatment will be analysed using the standard ANCOVA model.

Waist circumference

Change from baseline in waist circumference after 26 weeks of treatment will be analysed using the standard ANCOVA model.

Blood pressure (systolic and diastolic)

Change from baseline in blood pressure after 26 weeks of treatment will be analysed using the standard ANCOVA model.

Self-measured blood glucose (SMBG) 9-point profile

The following six endpoints from the 9-point profile will be defined:

- 9-point profile (individual SMBG values) [One endpoint]
- Mean of the 9-point profile, defined as the area under the profile (calculated using the trapezoidal method) divided by the measurement time [One endpoint]
- Prandial plasma glucose increments (from before meal to 90 min after for breakfast, lunch and dinner). The mean increment over all meals will be derived as the mean of all available meal increments [Four endpoints]

A linear mixed effect model will be fitted to the 9-point SMBG profile data. The model will include treatment, pre-trial anti-diabetic treatment, time, the interaction between treatment and time and the interaction between pre-trial anti-diabetic treatment and time as fixed factors and subject as random effect. From the model mean profile by treatment and relevant treatment differences will be estimated and explored.

Change from baseline after 26 weeks of treatment in mean of the 9-point profile and post-prandial increment endpoints will be analysed separately using the standard ANCOVA model.

Lipids

Total cholesterol, low density lipoprotein cholesterol (LDL cholesterol), high density lipoprotein cholesterol (HDL cholesterol), very low density lipoprotein cholesterol (VLDL cholesterol),

triglycerides, and free fatty acids after 26 weeks of treatment will be analysed separately by using the standard ANCOVA model. In these statistical analyses the endpoint will be log-transformed and so will the baseline covariate.

